9.1.1.6 Clinic Visit 4: Day 57 (-3/+7 days)

- Review and record any newly reported safety data including unsolicited AEs or other AEs (e.g., medically-attended AEs, SAEs).
- Record concomitant medications and vaccinations according to instructions in Section 7.6.
- Perform a symptom-directed physical examination (at the discretion of the Investigator; see Section 9.3.6).
- Measure vital signs (body temperature, pulse, blood pressure, see Section 9.3.6).
- Collect a blood sample for immunogenicity assessment (see Table 1) for binding antibody testing to RBD of S protein of SARS-CoV-2 (~6 mL blood) and SARS-CoV-2 viral neutralizing activity (~6 mL blood). (No testing of binding antibody to N protein of SARS-CoV-2 will be performed at this time point).
- Instructions for the subject:
 - Inform the subject that reporting of unsolicited AEs is complete.
 - Remind the subject to call the site immediately to report the following:
 - o If he/she experiences any concerning medical event.
 - Any medically-attended visits that are not routine visits for physical examination or vaccination, such as visits for hospitalization, an emergency room visit, or an otherwise unscheduled visit to or from medical personnel (medical doctor) for any reason.
 - Experience a serious medical event, have a change in overall health or be diagnosed with a new medical condition by a doctor. These should be reported regardless of the perceived relationship between the event and the trial vaccine.
 - Remind the subject to contact the site immediately if he/she has any of the symptoms suggestive of COVID-19. In addition, subjects will be messaged up to twice a week to provide a yes or no response to having COVID-19 symptoms. Those who respond "yes" will be contacted by trial staff for follow-up information if the Investigator considers the symptoms could potentially indicate a COVID-19 case (see Section 9.2.1 and Section 9.5).
 - The subject should also be reminded to contact the site immediately if he/she had a positive SARS-CoV-2 test performed outside of the site, whether they were symptomatic (COVID-19 illness) or asymptomatic at the time of the test.
- Complete the source documents and eCRF for this visit.

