2 STUDY SCHEMATIC AND SCHEDULE OF ACTIVITIES

Figure 1 Overview of HERALD Trial CV-NCOV-004

AV: authorized/licensed vaccines for preventing COVID-19; i.m.: intramuscular; SoC: standard of care.

Clinical Trial Protocol	CV-NCOV-004
CureVac AG	COVID-19 mRNA Vaccine

	Vaccination Period						Follow-up Period			
	Clinic Visit	Phone Call	Clinic Visit	Phone Call	Clinic Visit		Clinic Vis	it	Phone Call	Clinic Visit
Clinic Visit Number	1 ª	-	2	-	3	4	5	6	-	7
Visit Window (days)	n/a	-0/+0	-3/+7	-0/+0	-3/+3	-3/+7	-7/+7	-7/+7	-7/+7	-0/+21
Trial Day	1	2	29	30	43	57	120	211	302	393
Vaccination Day (Reference for post-vaccination time points)	-	1	1	29	29+14	29+28	29+91	29+182	29+273	29+364
Visit Week (Wk) / Month (M)			Wk 4		Wk 6	Wk 8	M 4	M 7	M 10	M 13
Signed informed consent	Х									
Inclusion/exclusion criteria	Х									
Demographics	Х									
Smoking information	Х									
Medical history	Х									
Medication/vaccination history ^b	Х									
Pregnancy test⁰	Х		Х							
Trial Vaccination										
Review criteria for delay or cancellation of trial vaccination ^d	Х		х							
Randomization	Х									
Administration of CVnCoV or placebo (observer-blinded administration)	х		х							
Safety Monitoring										
Physical examination ^e	Х									Х
Symptom-directed physical examination ^e			Х		Х	Х	Х	Х		
Vital signs ^{e,f}	Xf		Xf		Х	Х	Х	Х		Х
eDiary collection of solicited local and systemic reaction data, and unsolicited AEs ⁹	Х	х	х	х	Х	х				
Collection of following AEs:										
Medically-attended AEs ^h	Х	Х	Х	Х	Х	Х	Х	Х		

Table 1 Schedule of Trial Assessments and Procedures for Phase 2b - Immunogenicity Subset

Clinical Trial Protocol CureVac AG

	Vaccination Period					Follow-up Period				End of Trial
	Clinic Visit	Phone Call	Clinic Visit	Phone Call	Clinic Visit		Clinic Visi	t	Phone Call	Clinic Visit
Clinic Visit Number	1ª	-	2	-	3	4	5	6	-	7
Visit Window (days)	n/a	-0/+0	-3/+7	-0/+0	-3/+3	-3/+7	-7/+7	-7/+7	-7/+7	-0/+21
Trial Day	1	2	29	30	43	57	120	211	302	393
Vaccination Day (Reference for post-vaccination time points)	-	1	1	29	29+14	29+28	29+91	29+182	29+273	29+364
Visit Week (Wk) / Month (M)			Wk 4		Wk 6	Wk 8	M 4	M 7	M 10	M 13
 SAEs and AESIs^h 	Х	Х	Х	Х	Х	Х	Х	Х	Х	Х
 AEs leading to vaccine withdrawal or trial discontinuation^h 	Х	х	Х	х	Х	х	Х	х	х	х
Concomitant medication/vaccination ⁱ	Х	Х	Х	Х	Х	Х	Х	Х	Х	Х
COVID-19 Case Detection										
Case detection and collection of case information ⁱ	Х	Х	Х	Х	Х	Х	Х	Х	Х	Х
Antibody Testing ^k (n=1,200)										

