4.2 Endpoints

4.2.1 Primary Endpoints

Primary Efficacy Endpoint

• Occurrence of first episodes of virologically-confirmed {reverse transcription polymerase chain reaction (RT-PCR) positive} cases of COVID-19 of any severity meeting the case definition for the primary efficacy analysis.

Primary Safety Endpoints

All safety endpoints will be analyzed in all subjects, in subjects seronegative at baseline, and in subjects seropositive at baseline.

- Occurrence, intensity, and relationship of medically-attended AEs collected through 6 months after the second trial vaccination in all subjects.
- Occurrence, intensity, and relationship of SAEs and AESIs collected throughout the trial in all subjects.
- Occurrence of fatal SAEs throughout the trial in all subjects.
- Occurrence, intensity, and duration of each solicited local AE within 7 days after each trial vaccination in Phase 2b subjects.
- Occurrence, intensity, duration of each solicited systemic AE within 7 days after each trial vaccination in Phase 2b subjects.
- Occurrence, intensity and relationship of unsolicited AEs occurring within 28 days after each trial vaccination in Phase 2b subjects.
- Occurrence of AEs leading to vaccine withdrawal or trial discontinuation throughout the trial in all subjects.

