9.1.2.6 Phone Call: Day 57 (-3/+7)

The purpose of this phone contact is to inquire about the subject's general well-being and to assess safety since site visit on Day 43.

- During the phone call:
 - Review and record any newly reported safety data including unsolicited AEs or other AEs (e.g., medically-attended AEs, SAEs).
 - Record concomitant medications and vaccinations according to instructions in Section 7.6.
 - If the subject reports any concerning local or systemic reactions, or other AEs (e.g., medically-attended AEs, SAEs), these should be followed-up either by a phone call(s) or by an unscheduled site visit based on the judgment of the Investigator.

- Instructions for the subject:
 - Inform the subject that reporting of unsolicited AEs is complete.
 - Remind the subject to call the site immediately to report the following:
 - If he/she experiences any concerning medical event.
 - Any medically-attended visits that are not routine visits for physical examination or vaccination, such as visits for hospitalization, an emergency room visit, or an otherwise unscheduled visit to or from medical personnel (medical doctor) for any reason.
 - Experience a serious medical event, have a change in overall health or be diagnosed with a new medical condition by a doctor. These should be reported regardless of the perceived relationship between the event and the trial vaccine.
 - Remind the subject to contact the site immediately if he/she has any of the symptoms suggestive of COVID-19. In addition, subjects will be messaged up to twice a week to provide a yes or no response to having COVID-19 symptoms. Those who respond "yes" will be contacted by trial staff for follow-up information if the Investigator considers the symptoms could potentially indicate a COVID-19 case (see Section 9.2.1 and Section 9.5).
 - The subject should also be reminded to contact the site immediately if he/she had a positive SARS-CoV-2 test performed outside of the site, whether they were symptomatic (COVID-19 illness) or asymptomatic at the time of the test.
- Complete the source documents and eCRF for this phone call.

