9.3.3 Adverse Events

Definitions of AEs/SAEs, procedures for recording, evaluating, follow-up and reporting of AEs/SAEs/pregnancy/overdose, as well as assessments of intensity and causality of AEs, are provided in Appendix 10.

In Phase 2b, any AEs occurring during the 30-minute observation period after vaccination will be recorded in the eCRF. In Phase 3, only those AEs occurring during the 30-minute observation period after vaccination which constitute an AESI, medically-attended AE, or an SAE will be recorded in the eCRF.

It is important to note that COVID-19 illness and its complications/sequelae are consistent with the efficacy endpoints of the trial and, as such, should not be recorded as AEs. These data will be captured on the relevant eCRF pages for cases of COVID-19 illness that occur in the trial, which are expected outcomes of the trial. Only for any complications and sequelae of COVID-19 illness not mentioned on the COVID-19 summary form in the eCRF, an AE form needs to be completed. For consistency, the reporting procedure for COVID-19 cases in the open-label phase will remain as in the randomized observer-blinded phase despite the efficacy analysis is already completed. COVID-19 illness and its complications/sequelae as well as all symptoms listed in Section 9.2.1.4 will not be reported according to the standard expedited process for SAEs, even though the event may meet the criteria for an SAE. However please note that all fatal cases resulting from COVID-19 and its complications/sequelae and from all other events will be reported as SAEs and need to be reported to the CRO within 24 hours (see section Reporting of SAEs in Appendix 10).

Clinical Trial Protocol	CV-NCOV-004
CureVac AG	COVID-19 mRNA Vaccine

The reporting period for each type of AE and corresponding concomitant medication use is shown in Table 6.

АЕ Туре	Days 1 to 8	Days 29 to 36	Days 1 to 57	Day 1 to Month 6 ^a	Day 1 to EOT
Solicited AEs (Phase 2b)	Х	Х			
Unsolicited AEs (Phase 2b)			X		
Medically-attended AEs				Х	
SAE/AESI/COVID-19 fatal cases					Х
Any vaccination other than CVnCoV					Х
Any immune-suppressive/ modulating medication or other prohibited medication					Х
Non-serious intercurrent medical conditions that may affect the immune response to vaccination					Х

 Table 6
 Reporting Period by Type of Adverse Event

AE; adverse event; AESI: AE of special interest; AV: Authorized/licensed vaccines for preventing COVID-19; EOT: End of Trial; SAE: serious AE.

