9.3.3.2 Unsolicited Adverse Events and Serious Adverse Events

Unsolicited AEs occurring on the day of vaccination and the following 28 days will be recorded by Phase 2b subjects for each of the 2 trial vaccinations.

For all subjects in Phase 2b and Phase 3, medically-attended AEs will be collected through 6 months after the second trial vaccination or until the EOT if that occurs earlier than

Clinical Trial Protocol	CV-NCOV-004
CureVac AG	COVID-19 mRNA Vaccine

6 months after the second trial vaccination. SAEs and AESIs will be collected throughout the trial (see Table 6).

Medically-attended AEs are defined as AEs with medically-attended visits that are not routine visits for physical examination or vaccination, such as visits for hospitalization, an emergency room visit, or an otherwise unscheduled visit to or from medical personnel (medical doctor) for any reason. Clinic visits for COVID-19 testing resulting in negative test results are not considered as medically-attended visits, if there is no confirmed diagnosis and no prescribed concomitant medication.

The occurrence of AEs (serious and non-serious) will be assessed by non-directive questioning of the subject at each visit during the reporting periods specified in Table 6. Subjects should be instructed to report immediately any AEs with serious symptoms, subjective complaints or objective changes in their well-being to the Investigator or the site personnel, regardless of the perceived relationship between the event and the trial vaccine.

The Investigator will assess the relationship between trial vaccine and occurrence of each AE/SAE as well as the intensity (see Appendix 10).

Non-serious intercurrent medical conditions that may affect the immune response to vaccination will also be collected throughout the trial.

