12.7.1.1 Analysis of Unsolicited AEs

The following summaries of unsolicited AEs by SOC and PT are provided, separately for AEs occurring within the first 28 days after each vaccination, within the 28 days after any vaccination, and all reported AEs (including those reported later than 28 days after any vaccination):

- Occurrence of unsolicited AEs,
- Occurrence of related unsolicited AEs,
- Occurrence of unsolicited AEs by maximum severity (mild / moderate / severe),
- Occurrence of related unsolicited AEs by maximum severity (mild / moderate / severe)

Additionally, a summary of unsolicited AEs (excluding solicited AEs) occurring within the first 28 days after each vaccination and within 28 days after any dose that have a frequency of > 5% in at least one treatment arm (on PT level) by SOC and PT is provided. The summary is repeated for all reported AEs (including those reported later than 28 days after any vaccination).

Summaries of unsolicited AEs occurring within 28 days after each vaccination and within 28 days after any vaccination are provided based on the SAS 2. Summaries of all reported unsolicited AEs (including those reported later than 28 days after any vaccination) are provided based on the SAS.

Listings of unsolicited AEs and related unsolicited AEs are produced. These listings are excluding solicited AEs and flagging treatment emergent events.

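### Phase 2b subjects seen early at the Day 57 contact can have unsolicited AE collection closed up to 3 days before the dose-2 window of a primary safety endpoint ends, and the SAP tables do not show it

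*Protocol*

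**What the plan says.** Protocol 4.2.1 lists as a primary safety endpoint "Occurrence, intensity and relationship of unsolicited AEs occurring within 28 days after each trial vaccination in Phase 2b subjects". Protocol 9.3.3.2 sets the collection period, for each of the two doses: "Unsolicited AEs occurring on the day of vaccination and the following 28 days will be recorded by Phase 2b subjects".

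The schedules in Protocol section 2 (Tables 1 and 2) place the Day 57 contact at 29+28, that is, 28 days after dose 2, with a window of -3/+7 days. It is a clinic visit for the Immunogenicity Subset (9.1.1.6) and a phone call for the other Phase 2b subjects (9.1.2.6). Both sections carry the instruction "Inform the subject that reporting of unsolicited AEs is complete", and neither makes it conditional on the time since dose 2. Footnote g to both tables names Days 29, 43 and 57 as the diary reviews. The next scheduled contact is Day 120. Table 6 in Protocol 9.3.3 gives the reporting period for unsolicited AEs as Days 1 to 57.

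On the analysis side, SAP 12.7.1.1 provides "Summaries of unsolicited AEs occurring within 28 days after each vaccination" on SAS 2. SAP 12.7.1 bases percentages after the second vaccination on everyone in the set who received it. Neither section has person-time, a minimum follow-up rule, or a count of subjects with a short window.

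**The concern.** The nominal date of the closing contact is the last day of the endpoint window, so any early contact falls inside the window. A site that follows the protocol exactly can end a subject's unsolicited AE reporting before the period in 9.3.3.2 is over. The protocol avoids this for solicited AEs: recording is closed at Day 43 (-3/+3), at the earliest 14 - 3 = 11 days after dose 2, well past the 7-day solicited window. The unsolicited closure has no such margin.

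At stake is the absolute frequency of unsolicited AEs after dose 2. A reader of the tables cannot tell a subject observed for 25 days after dose 2 from one observed for 28. Protocol section 9 adds to this: in the pandemic setting visit windows are guidance and departures from them are not deviations, so contact timing would not be flagged by that route either.

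**Working it through.** **Inputs**
- Dose 2 nominally on Day 29; collection on the day of the dose plus 28 further days, so 29 calendar days (Protocol 9.3.3.2).
- Day 57 contact at 29+28, window -3/+7 (Protocol section 2, 9.1.1.6, 9.1.2.6).
- Dose-2 denominator: all dose-2 recipients in the set (SAP 12.7.1).

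**The plan's own figure.** 29 + 28 = 57, which matches both the schedule row and the end of the period in Table 6.

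**Earliest closure within the window.** 28 - 3 = 25 days after dose 2. Days 26, 27 and 28 fall after closure: 3/29 = 10.3% of the collection period (3/28 = 10.7% if the dose day is left out). A contact from dose 2 + 28 to dose 2 + 35 loses no full day.

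**Across all dose-2 recipients.** The documents do not say how many contacts were early, so the share is an assumption. If a share *f* of subjects is seen the full 3 days early, the uncovered fraction of dose-2 window person-days is *f* × 3/29:

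| Assumed share seen 3 days early | Window person-days uncovered |
|---|---|
| 10% | 1.0% |
| 25% | 2.6% |
| 50% | 5.2% |
| 100% | 10.3% |

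**Effect on a percentage of subjects (illustration).** Assume a constant hazard and no capture after closure. A true window incidence of 20% would be seen as 1 - (1 - 0.20)^(26/29) = 18.1% among subjects stopped 3 days early, and 30% as 27.4%. If 25% of subjects were early, the overall 20% would read 0.25 × 18.1% + 0.75 × 20% = 19.5%. If AEs cluster soon after vaccination, the shortfall is smaller.

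**The case against.** The strongest reply is that little is really lost. At dose 2 each Phase 2b subject is told to record for 28 days, with a reminder to continue at Day 43. At the Day 57 contact itself subjects are still asked to report concerning events, unscheduled medical visits, changes in health and new diagnoses. Medically-attended AEs, SAEs and AESIs continue to be collected (Protocol 9.3.1.2), and the Day 120 visit takes up newly reported AEs, with examples that are not exhaustive. This stands, and it confines the likely loss to mild, non-attended events in the last 1 to 3 days. It does not remove the conflict: the Day 57 instruction comes later than the others and explicitly ends the task.

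Two stronger readings are tempting and are not supported.

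- A reader might take Table 6 literally on trial days. Dose 2 may be given as late as Day 36, so a Day 57 cut-off would lose 28 - (57 - 36) = 7 days, and a Day 54 contact 28 - (54 - 36) = 10 days. But the schedule row ties the contact to dose 2, SAP 10.6.1 counts Visit Day 43 from the second vaccination, and the operative text defines the period relative to each dose. The Table 6 label is best read as nominal.
- A reader might infer that dose 2 is observed for less time than dose 1. The documents do not show that. Dose 2 may itself be given 3 days early, on Day 26, and SAP 10.5.4 assigns later unsolicited AEs to dose 2, so attribution to dose 1 can also end at 26 - 1 = 25 days.

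It is also fair to say that rewording a visit section in Protocol version 4.0 (November 2021) probably changes few data or none. That limits the protocol half of the remedy and leaves the SAP half untouched.

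**Conclusion.** The point holds as a small, definite conflict between a visit instruction and the window of a primary safety endpoint. For a subject seen early, collection can close up to 3 days before the dose-2 window ends, about 10% of it, and the SAP tables treat that subject as fully observed. The 3-day limit assumes that the Day 57 window runs from actual dose 2 and is kept to.

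The overall effect cannot be stated, because the share of early contacts is not given; the shares used above are assumptions. Its direction is a slight lowering of absolute dose-2 frequencies. A subject who already had the event before closure still counts, which reduces the effect on the headline percentage further.

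A reader might go on to infer a biased comparison of CVnCoV with placebo. The documents give no ground for that: the closing rule is the same in both arms, observers are blinded, and no formal safety test is planned.

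**What to change.** - **Protocol 9.1.1.6 and 9.1.2.6:** state that unsolicited AE reporting is complete only once 28 days after actual dose 2 have passed, and that a subject seen earlier keeps recording to that day, with review at a follow-up or the next contact. Making the window -0/+7 from actual dose 2 would serve equally.
- **Protocol Table 6:** reword the unsolicited AE column as running through 28 days after each dose, to match 9.3.3.2.
- **SAP 12.7.1.1, for data already collected:** report by arm the number of SAS 2 subjects whose Day 57 contact preceded dose 2 + 28 days, and repeat the dose-2 28-day table without them.

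The cost is wording in two visit sections and one table, plus one count and one repeat table from contact and dose dates. Where Day 57 contacts are already past, only the SAP item has practical effect.

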9.1.1.7 Clinic Visit 5: Day 120 (-7/+7 days)

• Review and record any newly reported AEs since the site visit on Day 57 (e.g., medically-attended AEs, SAEs).

- Record concomitant medications and vaccinations according to instructions in Section 7.6.
- Perform a symptom-directed physical examination (at the discretion of the Investigator; see Section 9.3.6).
- Measure vital signs (body temperature, pulse, blood pressure, see Section 9.3.6).
- Collect blood samples (see Table 1) for binding antibody testing to RBD of S protein
 of SARS-CoV-2 (~6 mL blood) and SARS-CoV-2 viral neutralizing activity (~6 mL
 blood). (No testing of binding antibody to N protein of SARS-CoV-2 will be performed
 at this time point).
- Collect pre-vaccination blood samples for genomic biomarkers (~6 mL blood) from subjects at selected site(s).
- Collect pre-vaccination blood samples for CMI (~32 mL blood) from subjects at selected site(s).
- Instructions for the subject:
 - Remind the subject to call the site immediately to report the following:
 - o If he/she experiences any concerning medical event.
 - Any medically-attended visits that are not routine visits for physical examination or vaccination, such as visits for hospitalization, an emergency room visit, or an otherwise unscheduled visit to or from medical personnel (medical doctor) for any reason.
 - Experience a serious medical event, have a change in overall health or be diagnosed with a new medical condition by a doctor. These should be reported regardless of the perceived relationship between the event and the trial vaccine.
 - Remind the subject to contact the site immediately if he/she has any of the symptoms suggestive of COVID-19. In addition, subjects will be messaged up to twice a week to provide a yes or no response to having COVID-19 symptoms. Those who respond "yes" will be contacted by trial staff for follow-up information if the Investigator considers the symptoms could potentially indicate a COVID-19 case (see Section 9.2.1 and Section 9.5).
 - The subject should also be reminded to contact the site immediately if he/she had a positive SARS-CoV-2 test performed outside of the site, whether they were symptomatic (COVID-19 illness) or asymptomatic at the time of the test.
- Complete the source documents and eCRF for this visit.

9.1.1.8 Clinic Visit 6: Day 211 (-7/+7 days)

The assessments and procedures are identical to those performed during Clinic Visit 5 on Day 120, except for the below.

 Collect blood samples (see Table 1) for binding antibody testing to RBD of S protein of SARS-CoV-2 (~6 mL blood); SARS-CoV-2 viral neutralizing activity (~6 mL blood); and binding antibody testing to N (nucleocapsid) protein of SARS-CoV-2 (~6 mL blood).

 Collect blood samples for genomic biomarkers (~6 mL blood) from subjects at selected site(s).

Collect blood samples for CMI (~32 mL blood) from subjects at selected site(s).

